5.2.2 Adverse Events

Adverse events will be coded using the Medical Dictionary for Regulatory Activities (MedDRA) Version 23.1 or higher.

Treatment-emergent adverse events will be tabulated and are defined as those adverse events that either start or worsen in severity on or after the date/time of first dose of study treatment.

Where dates are missing or partially missing, adverse events will be assumed to be treatment-emergent, unless there is clear evidence (through comparison of partial dates) to suggest that the adverse event started prior to the first dose of study treatment.

For summary tables, AEs with “Certain”, “Probable/Likely” and “Possible” relationship to the study drug, as well as all AEs judged as unassessable/unclassifiable, will be considered related. In listings the more granular classification will be used.

The following AEs are considered to be of special interest:

- Investigations (SOC):
 - Platelet count decreased (PT)
 - Neutrophil count decrease (PT)

Only platelet and neutrophils count decrease with hematological impact (i.e., at a given study visit, a decrease in the platelet or neutrophil count *equal to or more than a 30% from baseline's count*) are to be reported as an AE unless, in the opinion of the investigator, the decrease is non-clinically significant.

An overall overview of TEAEs will be presented, including number of patients and frequency affected by different types of AEs as well as the number of events for each category by treatment:

- Any TEAEs
 - TEAEs related to study drug
 - TEAEs leading to study discontinuation
 - TEAEs by severity (mild, moderate severe)
 - TEAEs by outcome
- Any Serious TEAEs (STEAEs):
 - STEAEs related to study drug
 - STEAEs leading to study discontinuation
 - STEAEs by severity (mild, moderate severe)
 - STEAEs by outcome
- Any TEAEs of special interest
 - Platelet count decreased
 - Neutrophil count decreased
- Any COVID-19 TEAEs

The total number of subjects with at least one TEAE and the total number of TEAEs will be presented overall and by treatment arm and tabulated by MedDRA SOC and PT. In addition, AEs will be tabulated by worst severity and worst relationship to treatment.

The same tabulations will be provided for TEAEs, TEAEs of special interest, TEAEs leading to study drug discontinuation, serious TEAEs (STEAEs) and STEAEs related to study medication.

Listings of subjects with STEAEs, deaths and STEAEs leading to discontinuation and individual narratives for these cases will be provided.

Adverse event summaries will be ordered in terms of decreasing frequency for SOC, and PT within SOC, in the vafidemstat treatment, and then similarly by decreasing frequency in the placebo treatment, and then alphabetically for SOC, and PT within SOC.

A listing by subject of all adverse events (including non-treatment-emergent events) will be provided. This listing will be presented by treatment and will include the following: center, subject identifier, age, sex, race, adverse event (SOC, PT, and verbatim term), date of onset, date of resolution, duration, severity, seriousness, action taken, outcome and causality.

If the start date/time of an adverse event (AE) is partially or completely missing, the date/time will be compared as far as possible with the date/time of the start of administration of study treatment. The AE will be assumed to be treatment-emergent if it cannot be definitively shown that the AE did not occur or worsen during the treatment-emergent period (worst-case approach). The following general rules will be used:

- If the start day is missing but the start month and year are complete, an AE will only be excluded as being treatment-emergent if the start month/year is before the month/year of first date of treatment or if the stop date/time is before last date of treatment.
- If the start day and month are missing but the start year is complete, an AE will only be excluded as being treatment-emergent if start year is before the year of first date of treatment or if the stop date is before first date of treatment.
- If the start date is completely missing, an AE will be considered treatment-emergent unless the stop date/time is before first date of treatment.

For other outcomes (e.g., date of vital signs collection) missing day will be filled in with the middle day of the month (e.g., day 15). If month and day are missing, they will be filled in with July 3rd (the middle day of the year).

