3. STUDY DESIGN

3.1. Overall Study Design

PORTICO is a double blind, randomized, placebo-controlled, adaptive 14-weeks Phase IIb trial to evaluate the efficacy and safety of vafidemstat in an adult borderline personality disorder (BPD) population.

The study will be a global, multicenter clinical trial conducted in approximately 20 study sites in Europe and the US.

Up to 188 participants will be enrolled and randomized in a 1:1 ratio (94 participants per arm) to active treatment with vafidemstat (1.2 mg) or placebo to yield an expected 150 completed study participants, since it is anticipated that 20% of participants will drop out of the trial.

An interim analysis will be performed after 90 participants have completed the specific week assessments (expected 108 patients enrolled after accounting for 20% dropout). Individuals that had the opportunity to complete their specific week visit, but were lost to follow-up, will also be included in the analysis, however, will not be included in the 90-patient count required for initiation of the interim analysis. The objective of this interim analysis will be to reassess the sample size based on the observed variability and effect sizes. If the conditional power is too low for both endpoints or the required sample size adjustment is considered to be too large, the study sample size will not be increased.

All recruited participants will have to complete a 2-week screening period to ensure study eligibility criteria, followed by 12-week double-blind period of active treatment (vafidemstat 1.2 mg/day) or placebo in a 1:1 randomization scheme; then, a 2-week follow-up participant-blind placebo run-out period ([Figure 1](#)). The purpose of the participant-blind placebo run-out period is to obtain safety and efficacy data after two-weeks without active study treatment. Participants will be kept treatment blinded in order to avoid efficacy assessment bias.

PORTICO will involve 9 study visits. Study visits are planned every two weeks after Baseline as reflected in the Schedule of Assessments and Procedures ([Table 1](#)).

The study treatment, vafidemstat or placebo, will be administered orally as single capsule in the early morning before the first daily food intake.

Participants will be asked to maintain a stable regimen of background pharmacological therapy, not to initiate any prohibited medications during the trial and to advise their study physician of any medication changes throughout the study.

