5. STUDY TREATMENT

5.1. Investigational Medicinal Product

5.1.1. Treatment Regimens

During the 12-week, double-blind, randomized, placebo-controlled *Treatment period*, from Visit 2 to Visit 8, participants will be randomized to one of these two treatment arms:

- Vafidemstat 1.2 mg/day fiw: participants will receive 1 capsule with 1.2 mg/day of vafidemstat from Monday to Friday and 1 capsule of placebo from Saturday to Sunday.
- Placebo: participants will receive 1 capsule of placebo per day.

During the 2-week, participant-blind, *Run-out Safety follow-up period*, from Visit 8 to Visit 9, all participants will receive 1 capsule of placebo per day.

Participants will be instructed to take the IMP orally as a single capsule, in the early morning before the first food intake (after overnight fasting conditions), once daily.

When attending planned study visits, participants must return to the investigator all the empty, partially used or unused blisters as well as the box and must take the IMP from the new box dispensed at the clinic, after all the corresponding blood extractions have been performed.

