7.3.1. Treatment emergent Adverse Events (TEAEs)

Adverse events (AEs) will be recorded during the study period from the signing of informed consent to the completion of the Follow-Up Visit.

Treatment emergent adverse events are defined as AEs that started after first intake of study drug. If no unambiguous assignment to treatment emergent is possible due to incomplete or missing dates, the AE will be considered as treatment emergent.

All information obtained on TEAEs will be displayed and tabulated by participant, treatment and dose (i.e. arm). Classification based in the Medical Dictionary for Regulatory Activities (MedDRA latest version available) by System Organ Class (SOC), Preferred Term (PT) and Low-Level Term (LLT) will also be provided.

For further information of definitions and reporting of AEs and SAEs, see Section 8.2.

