9.3.5. Secondary Efficacy Analysis

The same MMRM as for the primary analysis will be calculated without a formal confirmatory significance test. At each visit, estimates for the adjusted changes from baseline in both the treatment and the placebo arm (adjusted for individual differences and differences in baseline and therapy status) as well as for the difference in changes between the two arms will be presented, including 95% confidence intervals (CI).

Subgroup analyses may be performed on the following variables:

- Country or center
- Psychotherapy at baseline
- Sex

Further details will be outlined in the SAP.

Descriptive summary statistics will be presented for both, absolute values and changes from baseline by visit and treatment arm.

Efficacy endpoints results will be plotted versus time individually and using means (absolute values and change from baseline) calculated by actual treatment arm.

9.3.6.Secondary Safety Analyses

Safety endpoints will be analyzed throughout the study from baseline to week 14, including:

- Number and frequency of Treatment Emergent Adverse Events (TEAEs) by severity
- Number and frequency of Serious TEAEs by severity
- Number and percentage of withdrawn participants due to TEAEs
- Frequency of physical examination parameters, vital signs, and ECG parameters of potential clinical concern
- Frequency of clinical laboratory parameters of potential clinical concern throughout the study
- Columbia – Suicide Severity Rating Scale (C-SSRS) results
- Number and frequency of concomitant medication intake throughout the study

The change from baseline to specific week will be analyzed for the following safety endpoints:

- Change from baseline to specific week in physical examinations, vital signs, and ECG parameters
- Change from baseline to specific week in clinical laboratory parameters

More details to specific endpoints are provided below.

Adverse Events

The total number of participants with at least one AE and the total number of AEs will be presented overall and by treatment arm and tabulated by MedDRA SOC and PT. In addition, AEs will be tabulated by worst severity and worst relationship to treatment.

The same tabulations will be provided for TEAEs, TEAEs of special interest, TEAEs leading to study drug discontinuation, serious TEAEs (STEAES) and STEAEs related to study medication.

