3.2 Endpoints

The study endpoints are listed below – all information presented in *italics* is masked in the blinded study protocol.

Primary endpoints – Efficacy

- To evaluate the difference on the Clinical Global Impression-Severity focused on Agitation/Aggression (CGI-S A/A) from baseline to *Weeks 8-12*, between the active treatment and the placebo arm.
- To evaluate the difference on the Borderline Personality Disorder Checklist (BPDCL), from baseline to *Weeks 8-12*, between the active treatment and the placebo arm

Secondary endpoints – Efficacy

- To evaluate the change overtime on the CGI-S A/A
- To evaluate the change over time on the BPDCL
- To evaluate the difference on the following measures, from baseline to *Weeks 8-12*, as well as change over time, between the active treatment arm and the placebo arm:
 - a) Borderline Evaluation of Severity over Time (BEST)
 - b) Beck Depression Inventory – II (BDI-II)
 - c) State-Trait Anger Expression Inventory 2 (STAXI-2)
 - d) State-Trait Anxiety Inventory (STAI)

Secondary endpoints – Safety

- To evaluate the following safety endpoints throughout the study, from baseline to week 14, including:
 - a) Number, frequency and severity of Treatment Emergent Adverse Events (TEAEs)
 - b) Number, frequency and severity of Serious TEAEs
 - c) Number and percentage of withdrawn subjects due to TEAEs
 - d) Frequency of physical examination parameters, vital signs and ECG parameters of potential clinical concern throughout the study period
 - e) Frequency of clinical laboratory parameters (hematology, including platelets, and clinical chemistry) of potential clinical concern throughout the study period
 - f) Columbia – Suicide Severity Rating Scale (C-SSRS)
 - g) Use of concomitant medication throughout the study period
- To evaluate the change from baseline to *Week 12* of the following safety endpoints:
 - a) Physical examination, vital signs and ECG parameters
 - b) Clinical laboratory parameters (hematology, including platelets, and clinical chemistry)

Exploratory endpoints

- To evaluate the difference on the following measures, from baseline to *Weeks 8-12*, as well as change over time, between the active treatment arm and the placebo arm:

- a) Columbia – Suicide Severity Rating Scale (C-SSRS)
 - b) Number of visits to healthcare services outside of the trial (primary care, mental health services and ER visits)
 - c) Agitation-Aggression Psychiatric Inventory-Clinician Report (AAPI-CR)

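### TEAE tables pool twelve weeks of randomized treatment with the two-week all-placebo run-out, and no AE table shows the run-out separately

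*SAP*

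**What the plan says.** - **Start of the TEAE window.** SAP 5.2.2: TEAEs "are defined as those adverse events that either start or worsen in severity on or after the date/time of first dose of study treatment". Protocol 7.3.1: "Treatment emergent adverse events are defined as AEs that started after first intake of study drug". Neither sentence gives a stop.
- **Outer limit.** Protocol 7.3.1 has AEs recorded "from the signing of informed consent to the completion of the Follow-Up Visit". SAP 3.2 introduces the safety endpoints, with TEAEs first, as "To evaluate the following safety endpoints throughout the study, from baseline to week 14, including". Protocol 9.3.6 repeats the limit: "Safety endpoints will be analyzed throughout the study from baseline to week 14, including".
- **Run-out treatment.** Protocol 5.1.1: "from Visit 8 to Visit 9, all participants will receive 1 capsule of placebo per day".
- **Run-out purpose.** Protocol 3.1: the purpose "is to obtain safety and efficacy data after two-weeks without active study treatment".
- **AE displays.** SAP 5.2.2 tabulates by arm, SOC, PT, worst severity and worst relationship. SAP 5.2.3 adds listings, and SAP 5.2.11 adds the DMC displays. None of these is split by study period.

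**The concern.** The TEAE tables are where a reader looks for the AE profile of vafidemstat. As planned, an event with onset after the switch to placebo at Visit 8 is counted in the same cell as an event on active drug. Two different questions are merged: what happens while taking vafidemstat, and what happens after stopping it.

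The second question matters here. The trial's target symptoms are agitation and aggression, so events that appear when treatment stops are of interest in their own right. The protocol gives the run-out a safety purpose, yet no planned AE table uses it for that purpose. The two periods also differ in blinding: weeks 0 to 12 are double-blind, while the run-out is described only as participant-blind. Relatedness judgements from both nevertheless enter the same tables.

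**Working it through.** There is no AE rate or period-specific AE figure in the documents to reproduce. The check is of the text and the time windows, followed by an illustration on stated assumptions.

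**1. Are run-out events TEAEs?** The definition starts at first dose. The endpoint window ends at week 14, and AE collection ends at the Follow-Up Visit. The run-out lies between week 12 and week 14, so its events are inside the window.

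**2. Which column do they fall in?** SAP 4.5 summarizes the safety set as treated, with no period element, so a participant who took vafidemstat stays in the vafidemstat column after Visit 8. Placebo-arm run-out events count in the placebo column in the same way.

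**3. How much of the window is off drug?** Protocol Table 1 puts first dose at Day 1, Visit 8 at Day 85 ± 2 and Visit 9 at Day 99 ± 2.
- Randomized treatment: 85 − 1 = 84 days.
- Run-out: 99 − 85 = 14 days.
- Share: 14 / 98 = 14.3%.
- With the visit windows: from 10 / (86 + 10) = 10.4% to 18 / (82 + 18) = 18.0%.

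**4. What could pooling do?** This is illustration only. For a completer, with constant event rates relative to placebo of RR_on and RR_off, the pooled ratio is (84 × RR_on + 14 × RR_off) / 98.

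| Assumed RR_on | Assumed RR_off | Pooled ratio |
|---|---|---|
| 1.5 | 1 | 140 / 98 = 1.43 |
| 2 | 1 | 182 / 98 = 1.86 |
| 3 | 1 | 266 / 98 = 2.71 |
| 2 | 3 (1.5 times the on-drug rate) | 210 / 98 = 2.14 |

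The first three rows assume an immediate return to the placebo rate at Visit 8. The last assumes a rise after stopping. The direction reverses, and the pooled table cannot show which case applies.

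The SAP reports numbers of participants and events, not rate ratios, so here is the participant version. Assume a 20% placebo risk over 84 days and a doubled hazard on drug.
- At 84 days: active 1 − 0.8² = 0.36; ratio 0.36 / 0.20 = 1.80; difference 0.16.
- At 98 days with off-drug hazard equal to placebo: placebo 1 − 0.8^(98/84) = 0.229; active 1 − 0.8^(2 + 14/84) = 0.383; ratio 1.67; difference 0.154.

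Part of that fall comes from the longer window itself. Had the doubled hazard lasted 98 days, the ratio would be (1 − 0.8^(2 × 98/84)) / 0.229 = 0.406 / 0.229 = 1.77.

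**5. What is reported for weeks 12 to 14?** The by-subject AE listing in SAP 5.2.2 carries the onset date. Laboratory values (SAP 5.2.4), vital signs (5.2.5), C-SSRS (5.2.10) and CGI-S A/A (5.1.1) are summarized by treatment and visit, and all are scheduled at Visit 9. AEs have no equivalent summary.

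**6. How much run-out data will there be?** With the planned 75 completers per arm, 75 × 2 = 150 participant-weeks per arm in the run-out, against 75 × 12 = 900 on randomized treatment for the same people.

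**The case against.** Counting TEAEs to week 14 is a declared choice, made in both documents. An event caused by stopping vafidemstat is still a consequence of having been assigned it, so keeping it in that arm is cautious for safety. Completers in both arms pass through the same run-out, so there is no one-sided counting. The dilution figures need rates that nobody has, and they assume that drug effect ends at Visit 8. That is doubtful, because Protocol 1.2 describes vafidemstat as an irreversible inhibitor.

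All of this stands, and it rules out several stronger readings that a reader might infer:
- *TEAEs have no end.* The definition sentence has no stop, but week 14 and the Follow-Up Visit bound what is counted.
- *Withdrawal events cannot be recognised.* Onset dates are listed and serious TEAEs have narratives. Suicidality and agitation/aggression are also measured at Visit 9 and summarized by visit.
- *The run-out's safety purpose is abandoned.* It is partly served by the Visit 9 laboratory, vital sign and C-SSRS summaries. Protocol 3.1 does not promise an AE table by period.
- *The on-drug contrast is biased downward.* Step 4 shows that it could go either way.

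The objection does not reach one point. A listing is not a comparison between arms, and the by-visit summaries cover chosen measures, not AEs in general.

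**Conclusion.** The point holds as a gap in presentation; it does not make the planned tables invalid. AEs starting in the all-placebo run-out, 14.3% of a completer's TEAE window (about 10% to 18% with the visit windows), are tabulated with on-drug events. No planned table compares the arms on AEs in that period. The size and direction of any effect on the on-drug contrast are unknown, because the documents give no AE rates; the ratios above are assumptions. The share is for completers only, since participants who discontinue early do not enter the run-out. The efficacy analysis is not affected. The change is worth making because it is cheap and gives the run-out an AE analysis that matches its stated purpose.

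**What to change.** In SAP 5.2.2:
1. Keep the pooled week 0 to 14 TEAE tables.
2. Add tables by original arm that split AE onset or worsening into the double-blind period (first dose to last dose of randomized treatment) and the run-out/follow-up period. Cover all TEAEs, serious TEAEs and AEs of special interest.
3. State that run-out events are shown separately and are neither excluded nor presumed unrelated, given the irreversible mechanism.
4. Define the treatment-emergent period, a term the section uses without an end, and reconcile the partial-date rules. The first rule refers to the last date of treatment, while the next two refer to the first date.
5. Say how worsening is dated. Protocol 7.3.1 leaves worsening out of the TEAE definition. Protocol 8.2 lists start and stop dates, and 8.2.1 asks only for the worst severity. If no date of worsening is held, split on onset and say so.

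Cost: modest extra programming. For the onset split, the AE onset, dispensation and intake dates are already collected. Run-out counts will be small, so the added tables should be labelled descriptive and carry no formal test.

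### The first partial-date rule in SAP 5.2.2 tests the stop date against the last dose instead of the first, so adverse events that certainly began on treatment can be left out of the TEAE tables

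*SAP*

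**What the plan says.** SAP 5.2.2 defines TEAEs as "those adverse events that either start or worsen in severity on or after the date/time of first dose of study treatment". For missing or partly missing dates its default is to count the event, with one exception: "unless there is clear evidence (through comparison of partial dates) to suggest that the adverse event started prior to the first dose of study treatment". Neither statement refers to the last dose.

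Later in the same section, a lead-in says that partial start dates are compared with the start of study treatment, and that an event counts unless it can be shown definitively not to be treatment-emergent. The SAP calls this a worst-case approach. Three rules apply it:

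- **Start day missing, month and year known.** Excluded if the start month is before the month of first treatment, "or if the stop date/time is before last date of treatment".
- **Start day and month missing, year known.** Excluded "if start year is before the year of first date of treatment or if the stop date is before first date of treatment".
- **Start date wholly missing.** The rule reads: "an AE will be considered treatment-emergent unless the stop date/time is before first date of treatment".

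Protocol 7.3.1 takes the same line as the lead-in: "If no unambiguous assignment to treatment emergent is possible due to incomplete or missing dates, the AE will be considered as treatment emergent". SAP 5.5 declares no change from the protocol's planned analysis.

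**The concern.** A stop date before the first dose proves that an event was over before treatment began, so it is a sound reason to exclude. A stop date before the last dose proves nothing of the kind. Most transient events during a 12-week treatment period stop before the last dose. The first rule therefore excludes events that the TEAE definition includes, and it does so in the case where the most is known about the start date.

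The number and severity of TEAEs and serious TEAEs are secondary safety endpoints (Protocol 2.2, SAP 3.2). The overview table and the tabulations by system organ class and preferred term in SAP 5.2.2 rest on the TEAE classification. A rule that moves on-treatment events out of that class understates incidence in those tables.

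**Working it through.** The plan states no figure for this rule, so there is nothing to reproduce. The check has two parts.

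**1. One event under all three rules.** Assume first dose on 1 February and last dose on 25 April, which is day 84 in a non-leap year (28 + 31 + 25 = 84). An event has start 'March', day missing, and stops on 20 March. Onset lies between 1 and 20 March, that is, day 29 to day 48, so it is on treatment whatever the missing day is.

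| Start date recorded | Stop-date test | Result |
|---|---|---|
| Month and year | 20 March before last dose (25 April)? Yes | Excluded |
| Year only | 20 March before first dose (1 February)? No | TEAE |
| Nothing | 20 March before first dose? No | TEAE |

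The start-month or start-year condition does not exclude the event in any row, so the outcome turns on the stop-date test alone. Losing the month turns a non-TEAE into a TEAE, which no coherent rule should do.

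**2. How much of the affected subset is excluded.** Inputs: the treatment period is 12 weeks (Protocol 5.1.1: "During the 12-week, double-blind, randomized, placebo-controlled *Treatment period*, from Visit 2 to Visit 8"), so 12 × 7 = 84 days. Adding the 2-week placebo run-out gives 84 + 14 = 98 days of capsules. Event duration *d* is an assumption, shown over a range, and onset is taken as equally likely on each day.

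Let *L* be the last day of treatment. An event with onset on day *s* stops on day *s* + *d* − 1. The first rule excludes it when *s* + *d* − 1 < *L*, that is, when *s* ≤ *L* − *d*. The number of excluded onset days is therefore *L* − *d* out of *L*.

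| Assumed duration | *L* = 84 | *L* = 98 |
|---|---|---|
| 1 day | 83/84 = 98.8% | 97/98 = 99.0% |
| 3 days | 81/84 = 96.4% | 95/98 = 96.9% |
| 7 days | 77/84 = 91.7% | 91/98 = 92.9% |
| 14 days | 70/84 = 83.3% | 84/98 = 85.7% |
| 28 days | 56/84 = 66.7% | 70/98 = 71.4% |

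With the first date of treatment in the test, an event that starts on or after day 1 cannot stop before day 1, so the excluded count is 0 in every cell.

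These are shares of events with a missing start day and a known start month, year and stop date. They are not shares of all TEAEs.

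**The case against.** The strongest reply is that this is a slip of one word in a section whose governing statements already give the right answer: the TEAE definition, the general missing-date sentence, the worst-case lead-in and the other two rules all point to the first dose. A careful programmer might follow them. That is fair as a reading of intent. But the first rule is the specific operational instruction for this case, and two programmers could code it differently, each citing the SAP.

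It might also be said that the phrase limiting when an event may be excluded only sets a necessary condition. The second rule uses the same construction and is plainly an exclusion rule, so that reading does not rescue the first.

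Several stronger conclusions are tempting, and the documents do not support them:

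- **That the events disappear from the report.** They do not. SAP 5.2.2 lists all adverse events, including those that are not treatment-emergent, SAP 5.2.3 lists all serious ones, and Protocol 9.3.6 tabulates all AEs separately from TEAEs.
- **That serious TEAEs are materially undercounted.** Protocol 8.3 makes the event's start date mandatory in the initial SAE report, so a missing start day should be uncommon there.
- **That the DMC is misled.** The displays named in SAP 5.2.11 are titled as adverse event summaries and listings, not TEAE tables, and their shells are in a separate document. Use of the TEAE classification there is not shown.
- **That the treatment comparison is biased in a known direction.** That would need the frequency of missing start days and the duration of events by arm. The documents give neither.

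Protocol 8.2 also asks for a start date for every AE, so the affected subset may be small. This limits the expected impact but does not make the rule correct.

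**Conclusion.** The rule is wrong as written. It contradicts the TEAE definition, the general missing-date rule, the worst-case lead-in and both companion rules in SAP 5.2.2, and Protocol 7.3.1. Nothing elsewhere in either document makes the last date of treatment the right reference.

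The consequence is misclassification in the TEAE tables, always towards fewer TEAEs. It is confined to events with a missing start day, a known start month and year, and a stop date before the last dose. Events that are ongoing, or that stop on or after the last dose, are not touched by this condition. Within the affected type, roughly two thirds to nearly all on-treatment onset days are excluded, assuming durations of 28 days down to 1 day and uniform onset. The effect on total TEAE counts cannot be stated and may be small, particularly for serious events. Efficacy results are not affected.

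**What to change.** In the first partial-date rule of SAP 5.2.2, replace 'last date of treatment' with 'first date of treatment', so that all three rules use the same reference. Then confirm that the TEAE derivation code applies the first date, and rerun any TEAE output already produced under the rule as written. The cost is one word in the SAP and a check of the code. No new data and no design change are needed.
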